5. STUDY DURATION

The study duration is 12 months of recruitment plus 1 year follow-up for outcomes. Each study subject's participation will last approximately 1 year, including the follow-up for outcomes and adverse events.

5.1 Early Termination

Participation of this study is entirely voluntary. Not participating in this study will not change current standards of care, which are consistent with National Guidelines and international

standards. Patients have full autonomy to withdraw from the study if they are unwilling to continue the study for whatsoever reasons throughout the study period.

Before a subject is declared lost to follow-up, all efforts should have been made to contact the patient for a final assessment.

5.2 Criteria for Suspending or Terminating Study

Not applicable. This is an observational study and not an interventional study, the study aims to collect data of patients who had undergone the treatment, undergoing the treatment or will undergo the treatment. All the patients are managed under standard of care.

6. STUDY INTERVENTIONS

6.1 AmplatzerTM AmuletTM LAAO Device

The AmplatzerTM AmuletTM LAAO is a transcatheter, self-expanding device intended for use in preventing thrombus embolization from the left atrial appendage. The device is constructed from a nitinol mesh and consists of a lobe and a disc connected by a central waist. Polyester patches are sewn into both the lobe and disc to facilitate occlusion. The lobe has stabilizing wires to improve device placement and retention. The device has threaded screw attachments at each end for connection to the delivery and loading cables. The device has radiopaque markers at each end and at the stabilizing wires that permit Visibility during fluoroscopy.

7. STUDY EVALUATIONS/PROCEDURES

7.1 Clinical Evaluations

Data including demographics, CHA2DS2VASc score and HASBLED risk score and other medical history, surgical history, routine laboratory investigations, and medications will be collected during the screening.

7.2 Laboratory Evaluations and Specimen Collection

Not applicable. All blood investigations are as for routine clinical practice.

7.3 Case Report Form (CRF)

Please refer to Appendix.

7.4 Permitted or Non-permitted Medication

Medication assessments will be conducted at pre-discharge and all follow-ups. Patients will be assessed whether to be prescribed with anticoagulant or/and antiplatelet medications such as aspirin, clopidogrel, unfractionated heparin, LMW heparin, warfarin, dabigatran, rivaroxaban, apixaban and endoxaban, at various duration. The dose and planned duration will be determined by the investigator. There is no non-permitted medication which needs to be avoided by the patient after the implant.

All concomitant cardiac medications, at the time of screening, loading dose, and each visit will be recorded in the Case Report Form (CRF).

8. STATISTICAL CONSIDERATIONS

8.1 Details of statistical analysis

Descriptive statistics includes percentage, mean with standard deviation, or median with interquartile range will be reported, whichever appropriate. Categorical variables will be analysed using chi-square test or Fisher's exact test. Continuous variables will be analysed using independent (two variables only) or ANOVA test (more than two variables), or Mann-Whitney test (two variables only) or Kruskal-Wallis test (more than two variables) depending on the nature of underlying distributions. Time dependent outcome data will be analysed using Kaplan-Meier survival analysis.

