4.2 Study Outcomes

Primary outcome:

Safety:

- i. All-cause and cardiovascular mortality
- ii. Bleeding events
- iii. Pericardial effusion
- iv. Device dislocation and device related thrombus
- v. Access site complication

Efficacy:

- i. All cause and cardiovascular mortality
- ii. Ischemic stroke or transient ischemic attack
- iii. Systemic embolization
- iv. Occurrence of leak at the device supporting incomplete occlusion of the LAA.

Secondary outcomes

To compare the following with the European registries:

- i. Indication for LAA occlusion
- ii. Rate of technical and procedural success
- iii. Practice of antiplatelet and anticoagulation therapy

Exploratory outcome:

To explore on the cost effectiveness of LAAO with Amplatzer™ Amulet™ in the region.

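### Section 8.1 names Kaplan-Meier for time-dependent outcomes; for stroke/TIA, systemic embolization, bleeding and cardiovascular death, Aalen-Johansen cumulative incidence would be a small, free improvement

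*Protocol*

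**What the plan says.** Protocol Section 8.1 provides descriptive statistics (percentages, means, medians), tests for group comparisons, and one sentence on time to event: "Time dependent outcome data will be analysed using Kaplan-Meier survival analysis". It does not say which outcomes count as time dependent or how deaths are handled in the analysis of other outcomes. No competing-risk method is named anywhere in the protocol.

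Section 4.2 lists the primary outcomes as separate items. Mortality appears as "All-cause and cardiovascular mortality", under both safety and efficacy. Beside it stand "Bleeding events", "Ischemic stroke or transient ischemic attack" and "Systemic embolization", and the procedural and device outcomes "Pericardial effusion", "Device dislocation and device related thrombus" and "Occurrence of leak at the device supporting incomplete occlusion of the LAA". No composite with death is defined. Follow-up is 1 year (Section 5), and the sample size is 100, set by expected recruitment (Section 8.2).

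**The concern.** Death before a stroke, an embolic event or a bleed means that the event can no longer happen to that patient. Non-cardiovascular death does the same for cardiovascular mortality. Ordinary Kaplan-Meier censors such patients and so treats them as if they could still have the event later. One minus Kaplan-Meier then estimates a risk in a setting without competing death, not the share of patients expected to have the event within the year.

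The stake is modest. Estimating these 1-year outcomes is the primary objective, and the excess runs in one direction only. Two inconsistencies could appear in the report: a Kaplan-Meier risk slightly above the plain percentage for the same outcome, and cardiovascular and non-cardiovascular death risks that add up to more than all-cause mortality.

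**Working it through.** The protocol gives no calculated figure to reproduce. The check compares the two estimators.

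**Inputs**
- Event risks: 1.3% (stroke/TIA) and 1.6% (major bleeding) at 1 year, from the registry cited in Section 1.
- n = 100 (Section 8.2); horizon 1 year (Section 5).
- 1-year mortality *m*: not given in the protocol; assumed at 5%, 10% and 20%.

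**Direction.** With d events among n at risk at each event time, one minus Kaplan-Meier sums S_k(t−)·d/n, where S_k ignores the competing deaths. Aalen-Johansen sums S(t−)·d/n, where S counts them. Since S ≤ S_k, one minus Kaplan-Meier cannot be below Aalen-Johansen on the same data. They are equal when no competing death precedes an event.

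**Size, constant hazards.** Let Ld = −ln(1−m), which is 0.0513, 0.1054 and 0.2231. Solve Le/(Le+Ld)·(1−exp(−(Le+Ld))) = target cumulative incidence for Le; then one minus Kaplan-Meier is 1−exp(−Le).

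| | m = 5% | m = 10% | m = 20% |
|---|---|---|---|
| True 1.3% | 1.33% | 1.37% | 1.45% |
| True 1.6% | 1.64% | 1.69% | 1.78% |
| Relative excess | 2.6% | 5.3% | 11.5% |

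At 1.3% the excess is 0.03, 0.07 and 0.15 points. The standard error √(p(1−p)/100) is 1.13 points at 1.3% and 1.25 points at 1.6%.

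**Early events.** If half of a 1.3% risk falls at implant, before any death, one minus Kaplan-Meier is 1.317%, 1.335% and 1.375%, so the relative excess halves. If all events precede all deaths, the excess is nil.

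**Exact example.** Take 100 patients with complete follow-up, 2 events at 3 and 9 months, and evenly spread deaths in patients without the event. Aalen-Johansen and the plain percentage are both 2/100 = 2.00%. One minus Kaplan-Meier is:
- 5 deaths (1 before the first event, 4 before the second): 1−(98/99)(94/95) = 2.05%
- 10 deaths (3 and 8): 1−(96/97)(90/91) = 2.12%
- 20 deaths (5 and 15): 1−(94/95)(83/84) = 2.23%

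**Cause of death.** Assume half of deaths are cardiovascular, with constant hazards. Each Kaplan-Meier risk is F = 1−exp(−Ld/2) = 2.53%, 5.13% and 10.56%. The two sum to 5.06%, 10.26% and 21.11% against all-cause 5%, 10% and 20%. The excess is F² = 0.06, 0.26 and 1.11 points.

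**How often it shows.** In simulated studies of 100 patients with an assumed 5% loss to follow-up, one minus Kaplan-Meier was never below Aalen-Johansen. With events spread over the year, risks of 1.3% to 1.6% and mortality of 5% to 15%, it was strictly higher in about 62% to 75% of studies. With events confined to the first 7 days, the two were identical in about 85% to 94%.

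**The case against.** The strongest objection is that the protocol never says that deaths will be censored, nor that one minus Kaplan-Meier will be reported for stroke or bleeding. Such rules are commonly left to an SAP, which is not shown. This stands in part: the point is conditional on ordinary Kaplan-Meier practice, and an SAP may already settle it. But the protocol does name a method and draws no distinction between outcomes, so naming a better one is more than a request for missing detail.

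Second, the effect is immaterial: far below sampling error, in an exploratory study with no threshold or decision rule. This stands and sets the weight of the point.

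Third, Section 8.1 already allows percentages, which equal Aalen-Johansen when follow-up is complete. That also stands. With incomplete follow-up, Aalen-Johansen differs from the plain percentage too, so the change does not remove every second figure.

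Three stronger readings might be inferred, and the protocol does not support them:
- That every listed outcome goes to Kaplan-Meier without exception. The sentence contains neither an "all" nor a list of outcomes. Leak and device thrombus depend on imaging scheduled at 1 to 3 and 6 months (Appendix A) and are naturally reported as percentages; pericardial effusion is largely peri-procedural. These are hardly affected.
- That reported risks can never be too low. Sampling error, missed events, or a fatal event coded only as death can still lower an estimate.
- That one minus Kaplan-Meier is never below the proportion of patients who actually have the event. If 1 of 100 patients is lost and then has the only event, Kaplan-Meier gives 0% and the true proportion is 1%. Sections 5.1 and 14 provide for loss to follow-up and withdrawal. The guaranteed comparison is with Aalen-Johansen on the same data, or with the plain proportion when follow-up is complete.

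**Conclusion.** The point holds as a narrow, low-severity improvement for stroke/TIA, systemic embolization, bleeding and cardiovascular mortality. Kaplan-Meier remains right for all-cause mortality. If competing deaths are censored, the direction of the difference from Aalen-Johansen is a mathematical identity. Its size rests on the assumed mortality range and on events spread evenly over the year: at a 1.3% risk it stays within 0.15 points even at 20% mortality, roughly an eighth of the standard error (0.15/1.13). No conclusion of the study is likely to turn on it. The case for the change is coherence between reported figures at no cost.

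**What to change.** Replace the last sentence of Section 8.1 with:

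> All-cause mortality will be analysed by Kaplan-Meier. Other outcomes analysed as time to event (stroke/TIA, systemic embolization, bleeding, cardiovascular mortality) will be reported as the Aalen-Johansen cumulative incidence, with death before the event as the competing event (for cardiovascular mortality, non-cardiovascular death).

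The cost is two sentences. The only extra inputs are date and cause of death, which the mortality outcomes already require, and standard software computes the estimate. If an SAP exists, the same wording should appear there.

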8.2 Sample size

A sample size of 100 patients for the study. This is based on the estimated number of recruitments from the participating centers.

9. ASSESSMENT OF SAFETY

The investigator will monitor the occurrence of Serious Adverse Events (SAEs) for each subject during the study. For the purpose of this protocol, adverse events will be assessed from the date of informed consent form is signed until up to the end of follow-up.

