Assessments	
Subjects will be followed through 1 year post implant.
 
Required Testing
 
• Baseline evaluation: Informed consent, history and physical, 12-lead electrocardiogram (ECG), CHA2DS2-VASc score, HAS-BLED score, Modified Rankin Scale (mRS), medication assessment. Pre-procedural Imaging planning with TOE or CT scan• Procedure: TOE or ICE only when combined with baseline/pre-procedural imaging, and adverse event assessment• Post procedure/Pre-discharge: TTE, medication assessment, adverse event assessment• 1M to 3M: TOE or CT scan, medication assessment, adverse event assessment• 6M (+/- 2 weeks): TOE or CT scan, medication and AE assessment• 12 (+/- 6 weeks): Medication and adverse event assessment• Interim/unscheduled visits: per physician discretion

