3. ELIGIBILITY CRITERIA

This is an all-comer observational study and therefore all patients indicated for LAAO with the Amplatzer™ Amulet™ are eligible for the study. Subjects who meet criteria for eligibility will be asked to participate. Since this observational study is both retrospective and prospective, subjects who had their occluder implanted, been recently implanted or intended to undergo the procedure may be considered to participate in the study. Informed consent will be obtained for data collection purposes.

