4. STUDY DESIGN

4.1 Study Description

This is a both prospective and retrospective, multicenter observational study for all patient indicated for LAAO with the Amplatzer™ Amulet™ device.

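### Section 9 starts adverse event assessment at consent, which for already-implanted patients conflicts with the safety assessments scheduled at the procedure and before discharge

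*Protocol*

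**What the plan says.** **Window.** Section 9 opens with "The investigator will monitor the occurrence of Serious Adverse Events (SAEs) for each subject during the study" and then sets a single window: "adverse events will be assessed from the date of informed consent form is signed until up to the end of follow-up". Retrospective subjects are not mentioned.

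**Who is enrolled.** Section 4.1: "This is a both prospective and retrospective, multicenter observational study". Section 3: "subjects who had their occluder implanted, been recently implanted or intended to undergo the procedure may be considered to participate in the study". Sections 5.2 and 16 confirm that data on patients already treated are part of the study's purpose.

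**Scheduled safety assessments.** The Protocol Summary (Assessments) lists for the procedure "TOE or ICE only when combined with baseline/pre-procedural imaging, and adverse event assessment" and for the next step "Post procedure/Pre-discharge: TTE, medication assessment, adverse event assessment". In Appendix A the Safety Outcomes row is marked at implant, pre-discharge, 1-3, 6 and 12 months, with no limit to prospective subjects.

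**Primary safety outcomes.** Section 4.2 includes bleeding, pericardial effusion, access site complication and "Device dislocation and device related thrombus".

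**Consent.** Section 3, after admitting already-implanted patients, says "Informed consent will be obtained for data collection purposes". Section 11 ties consent to prospective data and requires it in writing before the intervention. Appendix A limits the consent row to prospective data collection.

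**The concern.** For a subject who consents before the implant there is no difficulty: the window is open when the procedure takes place. For a subject already implanted, the procedure and usually the index admission lie before any consent, and so outside the Section 9 window. Pericardial effusion, access site complication, device dislocation and procedural bleeding arise wholly or partly in that period. They are primary safety outcomes, and short-term safety is part of the primary objective in Section 2.

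A site that takes Section 9 as the rule for what to record would not count these events in already-implanted patients. If those patients stay in the denominator, the complication rate comes out too low, which favours the device. If some sites follow Section 9 and others follow Appendix A, the pooled rate mixes two capture windows. An analysis plan cannot repair this later, because events that were never recorded cannot be analysed.

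**Working it through.** The Protocol gives no figure to reproduce. The sample size of 100 in Section 8.2 rests on expected recruitment alone. The check is therefore a comparison of the text, followed by a bound on the effect.

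**Step 1. Apply each rule to each type of subject.**

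| Subject | Section 9 window | Protocol Summary and Appendix A | Consistent? |
|---|---|---|---|
| Consents before implant | Open at the procedure | Assess at procedure and pre-discharge | Yes |
| Already implanted, consents later (Section 3) | Opens after the procedure | Assess at procedure and pre-discharge | No |
| Already implanted, no consent (one reading of Section 11 and Appendix A) | No start date | Assess at procedure and pre-discharge | No |

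No section says which rule governs the Section 4.2 safety outcomes.

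**Step 2. Size of the possible undercount.** Let f be the share of already-implanted patients (not given), p1 the peri-procedural event risk in the other patients and p2 the risk in the already-implanted.

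- True pooled rate: (1 − f)·p1 + f·p2.
- Rate if Section 9 governs and all patients stay in the denominator: (1 − f)·p1.
- Relative understatement: f·p2 / [(1 − f)·p1 + f·p2].

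With p1 = p2 this equals f. It exceeds f whenever p2 > p1 and is smaller than f when p2 < p1. If Appendix A governs it is 0.

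Illustration with N = 100 and an assumed common rate p = 4%, so 100 × 0.04 = 4 expected events. Events lost are 100 × 0.04 × f:

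| f (assumed) | Events lost | Observed rate | Patients whose procedure falls in the window, 100 × (1 − f) |
|---|---|---|---|
| 10% | 0.4 | 3.6% | 90 |
| 25% | 1 | 3.0% | 75 |
| 50% | 2 | 2.0% | 50 |
| 75% | 3 | 1.0% | 25 |

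**Step 3. A separate matter: survival to enrolment.** Section 3.1 requires subjects to be able and willing to return for follow-up, so an already-implanted patient appears to have to be alive at enrolment. Section 8.1 specifies Kaplan-Meier analysis. Assume a constant hazard with 1-year mortality m, so S(t) = (1 − m)^t, and enrolment c years after implant for the share f. Kaplan-Meier counted from implant without delayed entry then gives

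(1 − f)·m + f·[1 − S(1)/S(c)].

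With m = 8%, f = 50%, c = 0.5: S(0.5) = 0.92^0.5 = 0.9592, and 0.5 × 0.08 + 0.5 × (1 − 0.92/0.9592) = 6.04%.

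- c = 0.25 or 0.75, f = 50%: 7.03% or 5.03%.
- f = 25% or 75%, c = 0.5: 7.02% or 5.06%.

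A simulation at m = 8%, f = 50%, c = 0.5 gave 6.06% without and 8.02% with delayed entry. All these values of m, f and c are assumptions.

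**The case against.** The strongest reply is that the Protocol can be read without any loss. Appendix A restricts only its consent row to prospective data; its Safety Outcomes row carries no such limit. Section 11 places consent before the intervention, so a window that opens at consent fits prospective subjects naturally. Section 9 is mainly about SAE monitoring, definitions and reporting, while the outcomes are defined in Section 4.2 and scheduled in Appendix A. To bar the procedural events of patients already treated would also defeat the purpose stated in Sections 5.2 and 16.

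Much of this stands. A reader might infer that the Protocol directs sites to discard peri-procedural events in already-implanted patients. The documents do not support that: Section 9 never says that it limits the Section 4.2 outcomes. But Section 9 does not confine itself to prospective subjects either; it speaks of each subject. The Protocol Summary uses the same term, adverse event assessment, for the procedure and pre-discharge. Section 9.3 tells investigators to record all SAEs once informed of them, but neither widens the window nor mentions events before enrolment. The benign reading is available but not stated.

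It is also fair to object that survival to enrolment is not caused by Section 9 and would remain after it was corrected, and that the handling of entry times is commonly left to an analysis plan. It is therefore kept here as a secondary, conditional point.

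**Conclusion.** The conflict is real for already-implanted patients and absent for those who consent before implant. It should be fixed, since a stated rule, if followed, would undercount primary safety outcomes. That sites will follow it in this way is not established.

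The size cannot be computed, because f is not given. The relative understatement lies between 0 (Appendix A governs) and about f (Section 9 governs, all patients kept in the denominator, equal event risk). A reader might take f as a firm ceiling. It is not: with higher risk among the already-implanted, the understatement exceeds f, and the Protocol gives no information on relative risk. The 4% rate and the values of f are illustrations only.

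Sections 3, 11 and Appendix A also leave unclear whether already-implanted patients consent. A reader might go on to infer that the Protocol is silent on whether they must be alive to enrol. Section 3.1 points towards yes. On that reading, and under the assumptions shown, a Kaplan-Meier mortality estimate from implant that ignores entry time would be too low.

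**What to change.** Reconcile Section 9 with the Protocol Summary and Appendix A by stating two things:

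1. The Section 4.2 safety outcomes are captured for every subject from the implant procedure onward. For already-implanted subjects, events before enrolment are abstracted from the medical record.
2. The consent-based window governs only ongoing AE/SAE reporting. It applies to every subject who consents, including those who consent after implant, so that nobody who consents and is then followed is left without an SAE window.

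Align Section 3 with Section 11 and Appendix A on whether already-implanted subjects consent.

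Secondary and conditional: where such subjects must be alive at enrolment, enter them at their enrolment date (delayed entry) in Kaplan-Meier estimates of mortality from implant, or report prospective and retrospective subjects separately.

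Cost: a short protocol clarification, some chart abstraction of index admissions and a little more analysis. The complication rate may look less favourable. Early mortality estimates become less precise, because delayed entry leaves fewer subjects at risk soon after implant.

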9.1 Serious Adverse Events (SAEs) Definitions

An AE is defined as any untoward medical occurrence, unintended disease or injury, or untoward clinical signs (including abnormal laboratory findings) in subjects, users or other persons, whether or not related to the investigational medical device. Lack of drug effect is not an adverse event.

An AE is classified as “serious” if the event:

- Led to death;
- Led to serious deterioration of a patient that:
 - Resulted in a life-threatening illness or injury;
 - Resulted in a permanent impairment of a body structure or a body function;
 - Required in subjects hospitalization or prolongation of existing hospitalization;
 - Resulted in medical or surgical intervention to prevent permanent impairment to a body structure or a body function.
- Led to foetal distress, foetal death or a congenital abnormality or birth defect.

Note: Planned hospitalization for a pre-existing condition, or a procedure required by the clinical study protocol, without serious deterioration in health, is not considered a serious adverse event.

